3.5.3.4 Hematology

Hematologic tests include: a complete blood count (CBC) consisting of a total white blood cell count (WBC) with differential (total neutrophil [including bands], lymphocyte, monocyte, eosinophil, and basophil counts), hemoglobin, and platelet count.

Differential counts will be converted to absolute values for CTC grade classification. For all the differential counts, percentages will be converted to absolute values, if necessary:

e.g. Absolute WBC diff (Wunit) = Absolute WBC (Wunit)*Relative WBCdiff(%)/100.

3.5.3.5 Biochemistry

Biochemistry includes the following parameters: urea or blood urea nitrogen (BUN), creatinine, sodium, potassium, calcium, albumin, direct and total bilirubin, alkaline phosphatase, AST,

[↓] Indicates that CTC grade increases as the parameter decreases, these parameters are to be included in the summary of minimum post-baseline lab parameters

ALT, glucose, magnesium, chloride, bicarbonate,, inorganic phosphate, urinalysis, thyroid function (T4, TSH) and cytokines (IL-6, IFN-γ).

3.5.4 Thyroid function tests

Thyroid function tests include the following parameters: Thyroid stimulating hormone, Thyroxine (total T4) and T4 Free. The change from baseline to worst value post baseline will be summarized.

3.5.5 Vital signs, weight and physical examinations

Vital sign assessments are performed in order to characterize basic body function. The following parameters are collected: weight (kg), body temperature (°C), pulse rate (beats per minute), systolic and diastolic blood pressure (mmHg).

Vital signs collected during on-treatment period will be summarized. Values measured during the post-treatment period will be flagged in the listings. The number and percentage of patients with notable vital sign values (high/low) will be presented by treatment. For analysis of vital signs, the clinically notable sign criteria are provided in Table 3-5.

Table 3-5 Criteria for notable vital sign values

Vital sign (unit)	Notable high value	Notable low value
Weight (kg)	increase >= 10% from baseline	decrease >= 10% from baseline
Systolic blood pressure (mmHg)	>=180 and increase from baseline of >=20	<=90 and decrease from baseline of >=20
Diastolic blood pressure (mmHg)	>=105 and increase from baseline of >=15	<=50 and decrease from baseline of >=15
Pulse rate (bpm)	>=100 and increase from baseline of >25%	<=50 and decrease from baseline of >25%
Body temperature (°C)	>= 39.1	

3.5.6 Electrocardiograms

The average of the ECG parameters at that assessment should be used in the analyses.

A listing of all ECG assessments will be produced by treatment and notable values will be flagged. In the listing, the assessments collected during the post-treatment period will be flagged.

The number and percentage of subjects with notable ECG values will be presented by treatment (see Table 3-6).

Table 3-6 Notable ECG values

ECG Parameter	Abnormal values
QT, QTcF and QTcB	New value of > 450 and ≤ 480 ms
	New value of > 480 and ≤ 500 ms
	New value of > 500 ms
	Increase from baseline of > 30 ms to ≤ 60 ms
	Increase from baseline of > 60 ms

Novartis	Confidential	Page 42
SAP final CSR	24-Jul-2020 (11:48)	CPDR001X2101
HR	Decrease from baseline >2 beats/min	25% and to a HR < 50
	Increase from baseline >25 beats/min	5% and to a HR >100
PR	Increase from baseline >25	5% and to a value >200 ms
	New value of > 200 ms	
QRS	Increase from baseline >25	5% and to a value >120 ms
	New values of QRS > 120	ms

3.5.7 ECOG

ECOG performance by treatment will be listed.

3.6 Pharmacokinetic data

Pharmacokinetic parameters of PDR001 will be determined using serum concentration only. Pharmacokinetic (PK) parameters for Phase II portion of the study will be determined for all PK-evaluable patients using non-compartmental method(s) using WinNonlin (Pharsight, Mountain View, CA).

All serum concentrations that are below the limit of quantification (BLQ) will be set to zero in the bioanalytical data.

The PK parameters displayed on Table 3-7 will be estimated and listed. All concentrations below the LLOQ, or any missing data, will be labeled as such in the concentration data listings. Concentrations below the LLOQ will be treated as zero in summary statistics. The "zero" values will be excluded from geometric mean calculation.

PAS will be used in all pharmacokinetic data analysis and PK summary statistics, except for the dose-exposure analysis in Phase I.

Table 3-7 Noncompartmental pharmacokinetic parameters

Variable	Definition (unit)
Cmax	Maximum observed concentration after drug administration [mass x volume-1] (ug/mL)
Tmax	Time to reach Cmax [time] (days)
AUC _(0-336h)	Area under the concentration-time curve from time 0 to 336 hours post-dose [mass x time x volume-1] for Q2W (ug*hr/mL or ug*day/mL)
AUC _(0-504h)	Area under the concentration-time curve from time 0 to 504 hours post-dose [mass x time x volume-1] for Q3W (ug*hr/mL or ug*day/mL)
AUC _(0-672h)	Area under the concentration-time curve from time 0 to 672 hours post-dose [mass x time x volume-1] for Q4W (ug*hr/mL or ug*day/mL)
AUCinf	The AUC from time zero to infinity (ug*hr/mL or ug*day/mL)
AUCtau*	Area under the concentration-time curve over the dosing interval [mass x time x volume-1] (ug*hr/mL or ug*day/mL)
Racc*	Accumulation ratio calculated as AUC _(0-336h) or AUCtau at cycle 3/ AUC _(0-336h) or AUCtau at cycle 1
CL	The total body clearance of drug from the serum [volume x time-1] (mL/hr)

Variable	Definition (unit)
Vz	The apparent volume of distribution during terminal phase (associated with λz) [volume] (mL)
Tlast	Time to last measurable concentration (days)
T1/2	Elimination half-life (days)

^{*}AUCtau will be estimated if data permits and in case of assessing the alternate dosing regimen. With cohorts of patients with Q3W dosing regimen, AUCtau (or AUC $_{0-504h}$) will be reported instead of AUC $_{(0-336h)}$ and also will be used to calculate Racc. With cohorts of patients with Q4W dosing regimen, AUCtau (or AUC $_{0-672h}$) will be reported instead of AUC $_{(0-336h)}$ and also will be used to calculate Racc.

The PK data may be combined with data from other trials for a population PK analysis and reported separately.

Early analysis of preliminary PK data may be conducted based on preliminary data prior to database lock. Planned dose instead of actual dose will be used; nominal time instead of actual elapsed time will be used, and no protocol deviations or other PAS exclusion criteria will be considered.

Descriptive statistics and graphical representation of PK

Descriptive statistics (n, mean, SD, CV% mean, geometric mean, CV% geo-mean, median, minimum and maximum) will be presented for all PK parameters (except Tmax and Tlast) by treatment. Zero concentrations will not be included in the geometric mean calculation. Since Tmax is generally evaluated by a non-parametric method, only n, median, minimum and maximum will be presented for this parameter. Any missing pharmacokinetic parameter data will not be imputed. Table 3-8 summarizes the PK parameters and the planned descriptive statistics.

Summary statistics will be presented for PDR001 serum concentrations at each scheduled time point. Median concentration versus time profiles will be generated. Descriptive graphical plots of individual serum concentration versus time profiles will be generated in the final CSR.

The PK analyses will use the actual dose received for each particular PK profile. Parameters relating to the PK profile (e.g. AUC and Cmax) will be summarized for data collected in Cycle 1 and Cycle 3.

Table 3-8 PK parameters – descriptive statistics

Parameters	Descriptive statistics	
Cmax, AUC _(0-tlast) (AUCtau if available or with alternate dosing regimen), and Racc (modified for alternate dosing regimen)	n, mean, SD, CV% mean, geometric mean, CV% geomean, median, minimum, and maximum.	
Tmax, Tlast	Median, minimum, and maximum.	
CV% mean = coefficient of variation (%) = 100*sd/mean CV% geo-mean = sqrt (exp (variance for log transformed data)-1)*100		

Listings for PK parameters will be presented.

The pharmacokinetic analysis set will be used for the PK analysis, tables and listings. Refer to Novartis Guidance on Pharmacokinetic Data Analysis and Reporting for other details. Pharmacogenetics/pharmacogenomics is not conducted in this study.

Dose proportionality

The analysis of dose proportionality will be conducted for AUCtau and Cmax of PDR001 using a power model on log-transformed scale. The log-transformed PK parameters will each be regressed onto a fixed factor for log (dose). The 90% confidence interval (CI) of the slope for each PK parameter will be computed from the model and presented in a summary table.

3.7 Biomarkers

3.7.1 Introduction

There may be circumstances when a decision is made to stop sample collection, or not perform or discontinue their analysis due to either practical or strategic reasons. Under such circumstances, the number of samples may be inadequate to perform a rigorous data analysis and the available data will only be listed and potentially summarized.

Additional analyses that may be performed after the completion of the end-of-study CSR will be documented in separate reports. The data analysis will be described in an addendum of the SAP or in a stand-alone analysis plan document, as appropriate.

3.7.2 Biomarkers and purpose of analysis

 Table 3-10
 Biomarkers and purpose of analysis

temic immune-cell population nune-response at baseline and

3.7.3 Biomarker data

The Full Analysis Set will be used for all biomarker analysis. Unless otherwise specified, all statistical analyses of biomarker data will be performed on patients with biomarker data. Assessment of associations between biomarker and safety data will be conducted using the Safety Set.

All subjects with evaluable PD measurements during phase I/II will be included in the data analysis, unless specified otherwise. Missing values will not be entered and will not be included in the analysis.

Table 3-11 Sample biomarker summary table

Biomarker	Time point	Sample	Method
BRAF V600 (melanoma and	At molecular pre- screening (if needed) or	Archival tumor sample OR newly obtained pre-	Immunohistochemistry
anaplastic thyroid cancer),	Screening	treatment tumor biopsy	
EGFR and/or ALK	At molecular pre- screening (if needed) or	Archival tumor sample OR	Immunohistochemistry
(NSCLC)	Screening (if fleeded) of Screening	newly obtained pre- treatment tumor biopsy	
Cytokines	C1D1 Pre-dose C1D15	Plasma	Immunoassay

Novartis Confidential Page 46 SAP final CSR 24-Jul-2020 (11:48) CPDR001X2101

		()	
Biomarker	Time point	Sample	Method
	C3D1 Pre-dose		
	150 days after last dose		

3.7.3.1 General data handling and preprocessing

The pre-dose assessment that is closest to the first dose of study treatment will be used as the baseline value. For assessments performed in tumor biopsies, fresh biopsy results will be used for baseline when both archived and fresh tumor samples are available. When more than one biomarker assay results are available for a subject at baseline (e.g. archival and freshly obtained sample), the highest quality assay results collected the closest prior to treatment start will be used. If there are multiple assay results of the same highest quality at baseline, the mean of the assay results will be used for all statistical analyses. For any other time point, if replicate assay results exist from the same time point, the mean of the replicate values will be used for all statistical analyses.

3.7.5 Biomarker data analysis

3.7.5.1 Categorization of continuous biomarker data

New categorical variables will be derived from continuous percent positivity using predefined thresholds, if available. In addition to the predefined threshold, other thresholds may be established by exploring the data collected within the current trial itself. If the pre-defined thresholds are not available, new categorical variables will be derived for biomarkers using the median levels as the threshold. Alternatively, multiple thresholds may be evaluated in an exploratory fashion and an optimized cut-point will be chosen to provide the most optimal separation for the efficacy outcome between patients below and above the cut-off.

Table 3-12 listed the selected threshold for biomarker expression levels of some IHC biomarkers.

Table 3-12 Predefined threshold for some IHC biomarker expression levels

Analyte	Parameter	Categories
PD-L1	Percent positive tumor	• Three-level category: 0 - < 1%; 1 - < 50%, ≥ 50%
		• Two-level category: 0 - < 1% (PD-L1-); ≥ 1% (PD-L1+)
CD8	Percent marker area	Two-level category: 0 - < 1% (CD8 low); ≥ 1% (CD8 high)

[figure not shown]

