The phase II part of the study will begin after the recommended phase 2 dose (RP2D) is determined. The primary objective of the phase II part is to evaluate PDR001 antitumor activity, in two “benchmark diseases”, NSCLC and melanoma, where response rates to nivolumab and pembrolizumab are known, as well as in TNBC in which antitumor activity was reported for pembrolizumab (Nanda 2014, Moreno and Ribas 2015). In response to evidence of clinical activity in a patient during the dose escalation phase of this study, a small group of patients with anaplastic thyroid carcinoma will also be enrolled to preliminarily assess any clinical activity in this very aggressive disease that lacks effective treatment options. Preliminary data from the early clinical studies of nivolumab and pembrolizumab, as well as the anti-PD-L1 antibodies, MPDL3280A and MEDI4736 indicate that PD-L1 protein expression both on tumor cells and on tumor-infiltrating immune cells correlates with clinical response to these agents (Topalian 2012, Weber 2013, Taube 2014, Powles 2014, Creelan 2014). PD-L1 expression will be measured for all patients enrolled, however, patients will not be selected for PD-L1 expression, since the response rates to nivolumab and pembrolizumab available in the literature are based on unselected populations. In these published studies, patients without PD-L1 expression also responded to treatment with anti-PD-1 immunotherapy (Topalian 2012, Hamid 2013b, Robert 2014, Motzer 2015).

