2.3.10 Subgroup analyses

Select summaries of efficacy will also be presented by treatment and will be based on PD-L1 expression with predefined thresholds (Section 3.7).

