3.7.5.3 Association between biomarkers and clinical outcome

PD-L1 and potential predictors of efficacy

Associations of PD-L1 expression and efficacy outcome (e.g. ORR, DOR and DCR) will be assessed using various approaches, such as tabulations of ORR by PD-L1 expression status, Kaplan-Meier plots and estimates of PFS by PD-L1 expression status, and OS estimates by PD-L1 expression status.

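### In the visible SAP text, continuous biomarkers are related to efficacy only as categories, which loses information in an exploratory analysis; add a continuous-scale model and keep the category displays

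*SAP*

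**What the plan says.** SAP 3.7.5.1 sets the rule for continuous markers. The first step is: "New categorical variables will be derived from continuous percent positivity using predefined thresholds, if available". SAP Table 3-12 supplies thresholds for two markers. PD-L1 (percent positive tumour) has a two-level version cut at 1% and a three-level version cut at 1% and 50%. CD8 (percent marker area) is cut at 1%. For anything else, "If the pre-defined thresholds are not available, new categorical variables will be derived for biomarkers using the median levels as the threshold". The same paragraph also allows other thresholds and, as an alternative, says that "an optimized cut-point will be chosen to provide the most optimal separation for the efficacy outcome". That last option is a separate problem and is not the subject here.

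SAP 3.7.5.3 gives the link to outcome, for PD-L1: "tabulations of ORR by PD-L1 expression status, Kaplan-Meier plots and estimates of PFS by PD-L1 expression status", with OS estimates by status as well. The list is introduced as examples, so it is not closed. SAP 2.3.10 adds that selected efficacy summaries "will be based on PD-L1 expression with predefined thresholds". On the measured scale, SAP 3.7.5.2 gives descriptive statistics. SAP 3.7.3 limits biomarker analyses to patients with biomarker data. No biomarker hypothesis, significance level, effect size or target power appears in the visible text.

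**The concern.** Percent positive tumour and percent marker area are graded measurements. A 1% cut puts a tumour just above 1% in the same class as one near 100%. The three-level PD-L1 version softens this but does not remove it. Protocol 2.2 reports that PD-L1 expression correlates with response, and also that "patients without PD-L1 expression also responded to treatment with anti-PD-1 immunotherapy". That section explains why patients were not selected on PD-L1 and does not argue for any scale, but a graded relation is plausible from it.

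Responders will be few. At the reference response rates they number about 12 in each NSCLC group, 18 in melanoma and 8 in TNBC, fewer where biomarker data are missing. A gradient is hard to see with such numbers, and a split makes it harder. A median cut also moves with the sample it is taken from. The SAP does not say whether the median is taken within a group or pooled, so the meaning of high and low is not fixed.

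**Working it through.** **1. The plan's own figures.** No biomarker power is stated. The only power-type figures for these group sizes are in Protocol Table 10-2, and exact binomial tails reproduce all 18 cells to 0.1 point. For example, P(X ≥ 12 | n=60, p=0.20) = 55.1%, P(X ≥ 18 | n=60, p=0.30) = 54.9% and P(X ≥ 8 | n=40, p=0.20) = 56.3%. They concern the observed-ORR rule, not biomarkers.

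**2. Inputs from the documents.** Group sizes are 60 (1a, 1b, 2), 40 (group 3), and 10 with possible extension to about 40 (group 4), from Protocol 4.1. Reference ORRs are 20% for NSCLC, 30% for melanoma and 20% for TNBC, from Protocol 10.8. Expected responders are 60 × 0.20 = 12, 60 × 0.30 = 18 and 40 × 0.20 = 8.

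**3. Assumptions, not in the documents.** Marker normal after transformation; logit P(response) = b0 + ln(OR)·x, with b0 set to give the stated ORR; OR per SD from 1.5 to 3; two-sided 5% test; everyone has biomarker data; ORR of 20% for group 4.

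**4. Large-sample check.** A median split of a normal marker multiplies the expected z-value by √(2/π) = 0.798. From 80% power: (1.960 + 0.842) × 0.798 = 2.236; 2.236 − 1.960 = 0.276; Φ(0.276) = 0.61. So 80% falls to 61%, a loss of about 19 points, which is near the largest possible.

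**5. Simulation.** Score test on x against the score test on x > sample median, 20,000 trials per setting. Entries are continuous versus split power in %, with the loss in points.

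| Setting | OR 1.5 | OR 2.0 | OR 2.5 | OR 3.0 |
|---|---|---|---|---|
| n=60, ORR 20% | 23 v 16 (7.1) | 52 v 35 (17.4) | 73 v 52 (21.4) | 85 v 64 (20.1) |
| n=60, ORR 30% | 29 v 20 (9.1) | 63 v 43 (19.9) | 84 v 64 (20.1) | 93 v 77 (16.1) |
| n=40, ORR 20% | 17 v 12 (4.5) | 37 v 24 (12.7) | 55 v 36 (19.0) | 67 v 47 (20.7) |
| n=10, ORR 20% | 7 v 5 (2.0) | 11 v 7 (4.4) | 15 v 9 (5.7) | 19 v 11 (8.7) |

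With no effect, the continuous test rejects in about 5% of trials in every setting. A rerun with 40,000 trials moved the largest n=60 loss to 21.8, hence about 7 to 22 points. Using ranks costs little: at n=60, ORR 20% and OR 2.0 / 2.5 / 3.0, power is 50 / 71 / 83%.

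**6. Fixed cuts.** At n=60, ORR 20%, OR 2.0, continuous power is 52%. A two-level cut gives 40% if 25% of patients lie above it and 19% if 75% do. In the rerun, a three-level ordered score cut at the 25th/75th, 33rd/67th, 40th/70th or 50th/75th percentiles gave 43 to 45%. The lower cut alone gave 19 to 36%. The three-level version therefore keeps more of the information.

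**7. PFS.** With about 80% events and HR per SD 1.25 to 1.8, a log-rank test on the median split loses 10 to 20 points at n=60 and 6 to 21 at n=40 against a Cox score test on x.

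**8. The opposite truth.** If response steps from 10% to 30% at the median, the split has more power: 42% v 34% at n=60 and 29% v 24% at n=40. Now let the step be at 1% (8% v 32% response), with 40 to 60% of patients at zero, the rest lognormal, and n=60. The 1% cut then has about 63 to 67% power against about 45 to 55% for log2(percent + 1). The size of that gap depends on the spread assumed for the positive values.

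**The case against.** The strongest reply is that the power figures describe a test the plan does not contain, and mostly a split it does not apply. PD-L1 is the only marker with a visible link to ORR or PFS, and it has fixed cuts. So does CD8, which has no visible efficacy analysis at all. The median rule is a fallback, and no visible text relates a median-split marker to efficacy. All of this stands, and it is why the median-split range is an illustration only. A reader might infer that the PD-L1 analysis loses 7 to 22 points; the documents do not support that, because the share of patients above 1% and 50% is not given.

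A reader might also infer that the plan has no continuous-scale analysis. The text does not allow that either. The list in SAP 3.7.5.3 is open, and nearby biomarker text is not visible (SAP 3.7.4, most of SAP Table 3-10, Protocol 10.6). What can be said is narrower: the visible text commits to none.

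It is also fair that the result depends on the shape of the effect. Step 8 shows that a true threshold favours the cut. This is a reason to keep the categories, but not to rely on them alone, since the shape is unknown.

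**Conclusion.** The point holds as a modest improvement to an exploratory analysis. In the visible text, continuous markers are categorised and PD-L1 is related to efficacy by category only.

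Under a log-linear effect, a normal marker and a two-sided 5% test, a median split costs about 7 to 22 points of power for response at n=60. It costs about 5 to 21 at n=40 with ORR 20%, and 2 to 9 at n=10. For the fixed PD-L1 cuts the loss cannot be stated without the prevalence; it is smaller for the three-level version than for the two-level one, and a step effect reverses it. Missing biomarker data would reduce n further.

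It would be tempting to call this an underpowered analysis, or to say that the medians are group-specific and so not comparable across indications. The plan states no power for these analyses, and SAP 3.7.5.1 does not say how the median is formed. Neither claim is made here.

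**What to change.** In SAP 3.7.5.3, make the main association analysis for PD-L1, and for any other continuous marker related to efficacy, a model on a scale fixed before the analysis: log2(percent + 1) or rank. Use logistic regression for confirmed response and Cox regression for PFS, by disease group, and report the odds ratio or hazard ratio per unit with its confidence interval. Keep the PD-L1 1%/50% and CD8 1% tables and the Kaplan-Meier plots as descriptive displays. In SAP 3.7.5.1, replace the median default by this analysis for markers without a predefined threshold.

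The cost is SAP wording and one extra model per marker and endpoint, on data already collected. The drawbacks are that the scale must be chosen in advance, that effects are read per unit instead of as positive versus negative, and that with about 8 responders the interval will be wide and only the marker itself can be fitted. Because this SAP version serves the final CSR, it should also record whether marker data had been seen when the scale was chosen.

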3.7.5.2 Descriptive statistics for biomarker

The biomarker data will be listed for each subject for all time points and ordered by the treatment group. For each measurement, the mean, standard deviation, median, minimum, maximum, and number for each treatment group at each time point will be reported.

If repeated biomarker assessments are made at multiple visits e.g. pre and post treatment, absolute and relative change (percent change) from baseline will be calculated for each subject and reported by treatment group. If there are post-baseline data available, longitudinal plots showing mean changes may be generated only if post-baseline data for at least 3 patients in the same treatment group are available.

Counts (and percentages) by categories defined by the predefined thresholds will be reported at each time point and treatment group.

Furthermore, the following specifies the examples of outputs that will be produced to incorporate multiple biomarker types:

at each time point and change from baseline will be listed by patient and summarized (when sample size is sufficient) using descriptive statistics by treatment group.

The EGFR, ALK and BRAF tumor mutation statuses will be summarized using
descriptive statistics by treatment group. If a subject provided written documentation of
these tumor mutation statuses to enter the screening phase, the provided results will be
used. If not, the tumor mutation statuses from the molecular pre-screening assessment
will be used.

